13. ANALYSIS

The trial has sufficient resources to enroll at least 176 participants who will be randomly allocated to 1 of 2 sequences for each of the two groups: (1) the Self-Directed group or (2) the DASH intervention group.

Power and sample size

A. Aim 1 Immediate Effects: Clinical Outcomes (Effectiveness)

- 1. Primary endpoint: The proposed study is powered for office SBP. Based on the 12-week SBP means and variances from the DASH-Sodium trial,⁶ with 75 people in each arm, we will be able to detect a difference in SBP of -5.8 mm Hg (type 1 error of 0.05, power of 0.85). The 12-week between-group difference in SBP in DASH-Sodium was -8.9 mm Hg.
- 2. Secondary endpoints: We will have adequate power to detect small differences (i.e., <15%) in wake-time SBP, BMI, cholesterol, triglycerides, and hemoglobin A1c.

B. Aim 2 Immediate Effects: Behaviors (Adoption)

We will be able to detect changes of 13.0% to 29.5% in self-reported fruit and vegetable intake, urine sodium and potassium, and home-prepared dinners per week. These differences are smaller in magnitude than actual differences observed in prior trials.^{29,30}

Analysis Plan (RE-AIM Framework)

Reach. As in prior work, we will quantify recruitment yields and engagement. 52,53

Effectiveness & Adoption. The analysis will be conducted by the Statistical Core under the intent-to-treat principle for both effectiveness and adoption endpoints. The residual distribution of all outcomes will be checked for normality and log-transformed where appropriate. For the Primary Aim, we will use generalized estimating equation (GEE) models with a treatment-by-visit interaction term. The visit term will be used to compare changes on office SBP between 3 months versus baseline, 6 months versus 3 months, and 6 months versus baseline with a product (interaction) term to compare changes across intervention assignment (DASH vs self-directed shopping). Models will be adjusted for ZIP code or baseline blood pressure in sensitivity analyses. Continuous variables will be analyzed with a Gaussian distribution, identity link, while dichotomous variables will be analyzed with a binomial distribution, logit link.

Implementation. Quality-of-life and cost data will be used to analyze health economic data and budget impact, based on cost per HTN case prevented and 10-year cost per quality-adjusted life-year gained.

Maintenance. In qualitative analyses, a coding dictionary will be developed and implemented based on review of the transcripts' content and interview questions. Codes will denote content of questions, GTE and PRISM domains/principles, and concepts naturally emerging from discussion. During the coding process, inter-rater reliability will be established by comparing the agreement in coded text with 20% of the transcripts between coders. Coding differences will be resolved through consensus through regular and iterative discussions. A qualitative database will be compiled, coded, and analyzed using qualitative software (NVivo). We will use text retrieval and grouping functions on specific codes and combinations of codes for a particular topic and summarize the issues, agreements, and disagreements in content for each item. This process will result in a list of themes related to intervention acceptability³¹ and determinants (barriers and facilitators) of DASH eating plan sustainability. As we summarize and interpret, we will identify findings or patterns among themes and will review data for statements that directly confirm or discredit our interpretations.⁶² This theme-focused analysis will provide qualitative data to be integrated with our quantitative findings and guide refinement of the intervention.

Missing data

Based on the existing literature, we will employ recommended strategies to address missing data. ^{63,64,65,66} However, every effort will be made to collect outcome data on all participants.

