2. SPECIFIC AIMS

Aim 1: Determine the effectiveness of dietitian-assisted, virtually ordered, home-delivered DASH groceries on systolic blood pressure (SBP) among Black adults with elevated blood pressure (BP) or untreated stage 1 or 2 hypertension. *H1.1* DASH groceries will lower SBP (primary outcome) compared to self-directed grocery shopping after 3 months and effects will be maintained at 6 months post-randomization.

Aim 2: Determine the immediate and sustained effects of dietitian-assisted grocery shopping on families' adoption of the DASH eating plan and frequency of home-prepared meals versus out-of-home dining, 3-, 6-, and 12-months post-randomization. H2.1 DASH groceries will \uparrow DASH adherence (self-report, \downarrow urine sodium & \uparrow potassium) and $H2.2 \uparrow$ home-prepared meals and \downarrow out-of-home dining (self-report, quantified using the SHoPPER questionnaire).

Aim 3: Evaluate the reach, maintenance, and cost-effectiveness of the intervention up to 12 months post-randomization using a RE-AIM framework and mixed methods. *H3.1*: Reach, quantified during our recruitment campaign, will be high. *H3.2*: A 3-month, dietitian

assisted program will be cost-effective compared to self-directed grocery shopping at 1 year. *H3.3:* Identifying barriers and facilitators in qualitative interviews will enhance scalability.

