- 3. Food shopping, meal preparation, and dining behaviors and habits will be assessed via the interviewer-administered SHoPPER questionnaire^{38,39} at the (SVa, RZ, FV1a, FV2a, FV3), which has been adapted for this study. A 24-hour recall will also be conducted by a certified study staff member at visits SVb, FV1b, and FV2b, using the Automated Self-Administered 24-Hour (ASA24®) Dietary Assessment Tool.
- 1. Other Measures (Questionnaires): The Accountable Health Communities Health Related Social Needs Screening Tool⁴¹ will be interviewer-administered at SVa to examine the prevalence of health-related social needs among participants at baseline. The Perceived

Stress Scale⁴¹ will be administered at SVb, FV1b, FV2b, FV3 to assess the participant's feelings on stress. In addition, all participants will complete the 2-item Hunger Vital Sign, ^{49,50} a food insecurity screener, at SVa, FV1a, FV2a, and FV3. The IPAQ⁵¹ will be used at SVa and RZ with the Mifflin-St. Jeor estimator (along with age, sex, and BMI) to estimate resting metabolic rate (average across visits) to determine the amount of groceries. A Diet Symptoms Questionnaire adapted from the DASH-Sodium trial will be administered at SVa, FV1a, FV2a, and FV3 to document any dietary reactions, including light-headedness, bloating, headaches, or fatigue. Medication lists will be assessed via pill bottle evaluation at SVa and updated throughout the study (RZ, FV1a, FV2a, and FV3). We will closely monitor for the addition of anti-HTN medications between visits. Grocery order sheets from the intervention phase will be used to compare the micronutrient profile of the intervention, using ESHA software (Salem, OR) and for exploratory stratified analyses based on the distribution of specific food items or micronutrients (e.g., potassium).

RE-AIM Secondary Endpoints: Reach & Implementation (Specific Aim 3)

- 1. Reach: We will track referrals, participation rates, and recruitment yields as in prior work. 52,53
- Implementation: The SF-12 will assess global health-related quality of life at SVb, FV1b, FV2b, and FV3. A standard intervention costing instrument will gather costs of groceries and dietitian salary and effort gathered over study phases through structured interviews of staff, financial records, and direct observation. Beyond these instruments we will also track process information (e.g., Run-in Visit results), that can be used to access scalability.

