11. INTERVENTIONS

Distribution and adherence

Overview: Participants will be assigned to one of two 3-month interventions: (1) dietitian-assisted, DASH-patterned, home-delivered groceries ordered weekly through Amazon Fresh or Instacart over 12 weeks or (2) self-directed grocery shopping (monthly stipend and DASH eating plan brochure) over 3 months (referent). All participants will receive materials for addressing food insecurity, a set of measuring cups and spoons, a digital food thermometer, and page one of NHLBI's "Your Guide to Lowering Your Blood Pressure with DASH." 18,60

Self-Directed Shopping: These participants receive an unrestricted stipend of \$500/month (at 4, 8, and 12 weeks). There will be a call with the dietitian at week 8 to establish contact, check on the payments, and schedule FV1.

Dietitian-Assisted DASH Grocery Intervention: Participants randomized to the DASH grocery intervention will participate in weekly calls with the study dietitian. These calls will serve three purposes: (1) order groceries for the week, (2) assess compliance from the prior week's order, and (3) allow for education on fundamentals of healthy grocery shopping, meal storage, preparation, and in-home eating (**Table 3**).

Table 3: Curriculum
Module 1: Principles of DASH
Module 2: Food storage to reduce waste
Module 3: Sodium and potassium: What do they mean for your health?
Module 4: Quick food safety tips
Module 5: Enhance your favorite meal and explore something new
Module 6: Understanding nutrition labels
Module 7: Strategies to increase fruits and vegetables servings
Module 8: Quick and healthy meal prep
Module 9: DASH at Home
Module 10: DASH at restaurants and special events/holidays
Module 11: Smart Shopping
Module 12: Recap and DASH principles

Participants will also be provided instructions on how to receive food deliveries, food storage strategies to avoid spoiling, meal preparation tips, and example recipes that incorporate cultural foods and dishes. We will also prepare 24 instructional cooking videos (10-15-minute duration)

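### H3.2 claims cost-effectiveness at 1 year, but the plan's only cost-per-QALY analysis has a 10-year horizon and the handling of the $1,500 control stipend is not stated

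*Protocol*

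**What the plan says.** Protocol section 2 sets Aim 3 as "Evaluate the reach, maintenance, and cost-effectiveness of the intervention up to 12 months post-randomization using a RE-AIM framework and mixed methods". Under it, H3.2 states that the 3-month dietitian-"assisted program will be cost-effective compared to self-directed grocery shopping at 1 year". Section 4 likewise describes the economic evaluation as covering the 12-month study.

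The economic analysis itself is one sentence in section 13, under Implementation. Quality-of-life and cost data will feed a health-economic and budget-impact analysis "based on cost per HTN case prevented and 10-year cost per quality-adjusted life-year gained".

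For the data, section 7 (RE-AIM Secondary Endpoints) schedules the SF-12 "at SVb, FV1b, FV2b, and FV3. A standard intervention costing instrument will gather" the costs "of groceries and dietitian salary and effort gathered over study phases through structured interviews of staff, financial records, and direct observation". Section 11 describes the comparator: "These participants receive an unrestricted stipend of" $500 a month, paid at weeks 4, 8 and 12.

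The SAP introduction places quality of life outside the analysis it describes, and no SAP section deals with costs, utilities or QALYs.

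**The concern.** H3.2 is a comparative claim with a stated time point. Testing it needs an incremental cost and an incremental effect between the two arms at 12 months, and a rule for what counts as cost-effective. The plan gives a QALY ratio at a different horizon and does not say which control-arm costs enter the difference. Perspective, discount rate, willingness-to-pay threshold, the mapping from SF-12 to utility and the 10-year extrapolation model are not given either.

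Protocol section 3 presents the findings as possible evidence for a change in national food-assistance policy if the program works at an affordable cost. An economic result put to that use should have its horizon and comparator cost fixed before the data are seen. If they stay open, they can be settled after unmasking, and both can move the answer materially.

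**Working it through.** The documents give no economic figure (no ratio, threshold, incremental cost or QALY gain), so there is nothing of the plan's own to reproduce. The check compares the horizons and then sizes the two open choices.

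**1. Horizons**

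| Item | Horizon | Source |
|---|---|---|
| H3.2 | 1 year | Protocol 2 |
| Aim 3 | up to 12 months | Protocol 2 and 4 |
| Cost per QALY | 10 years | Protocol 13 |
| Cost per hypertension case prevented | not stated | Protocol 13 |
| SF-12 | baseline, 3, 6 and 12 months | Protocol 7 |
| Office BP | baseline, 3 and 6 months (second follow-up at 5-6 months) | Protocol 7 |
| 12-month visit | telephone | Protocol 7 |

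The case-prevented measure cannot fill the 1-year slot. A BP-defined case needs BP, and none is taken at 12 months. Medications are reviewed at the telephone visit, but that would identify treatment started, not a BP-defined case. The trial also enrols people who already have untreated hypertension, for whom a prevented case is not defined.

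**2. Stipend**

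Stipend per control participant = 3 x $500 = $1,500. With 176/2 = 88 controls, the total is 88 x $1,500 = $132,000.

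Incremental cost per participant = groceries + dietitian time - stipend (if counted).

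This trial's grocery cost is not stated, so the following is an illustration with assumed inputs:
- Groceries: $105 to $300 a week for 12 weeks. The lower figure is what the earlier gout grocery trial provided (Protocol 3); the upper figure is assumed.
- Dietitian contact: one first session of 60-90 minutes plus 11 calls of about 30 minutes (Protocol 11). That is (60 + 330)/60 = 6.5 hours to (90 + 330)/60 = 7.0 hours, midpoint 6.75.
- Dietitian rate: $40 to $80 an hour, assumed. The control arm's single week-8 call is ignored.

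| | Low | High |
|---|---|---|
| Groceries | 12 x $105 = $1,260 | 12 x $300 = $3,600 |
| Dietitian | 6.75 x $40 = $270 | 6.75 x $80 = $540 |
| Incremental cost, stipend not counted | $1,530 | $4,140 |
| Incremental cost, stipend counted | $30 | $2,640 |

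Leaving the stipend out raises incremental cost by exactly $1,500 in every row of assumptions, so it makes the program look less cost-effective. At the low end the choice decides whether the program is close to cost-neutral.

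**3. Horizon**

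Take a one-off cost in the first year, no later cost offsets, and a QALY gain of q in year 1. If the same annual gain lasts k years in total, undiscounted 10-year QALYs are kq, and cost per QALY is k times lower than at 1 year.
- Gain ends by 12 months: k = 1, no difference.
- Gain lasts 10 years in full: k = 10.
- The same, discounted at an assumed 3%: the annuity factor is (1 - 1.03^-10)/0.03 = 8.53. Discounting year 1 in the same way gives 8.53/0.971 = 8.79.

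The range is therefore 1 to about 10, and the assumed persistence drives it far more than the discount rate does.

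**The case against.** The strongest reply has four parts.

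First, section 13 plans more than a 10-year QALY ratio: it also names cost per case prevented and budget impact. A reader might infer that H3.2 goes wholly untested. The documents do not support that, because the SF-12 data for a 12-month analysis will be collected. What stands is narrower: no analysis at that horizon is specified, and the case-prevented measure cannot supply one from BP.

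Second, the stipend is unnamed, not excluded. It is a fixed amount in both documents and financial records are a listed cost source, so a reader who infers that it will be dropped, or that the incremental cost must be wrong, goes beyond the text. Whether an unrestricted cash payment is a cost or a transfer depends on the perspective. For a policy of sponsoring groceries, the realistic alternative need not include $500 a month. This stands, and it is the reason to report both versions.

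Third, it is tempting to say the 10-year ratio flatters the program about ninefold. That needs the gain from a 3-month program to persist in full for a decade, which nothing in the documents supports. Nor do the two gaps push the same way: omitting the stipend counts against the program, while the long horizon can favour it. The net direction is unknown.

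Fourth, a 10-year figure from a 12-month study is openly a modelled one, and extrapolating is not in itself a fault. The SAP also says plainly that quality of life is outside its scope. Both are fair, but neither supplies the 1-year analysis.

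**Conclusion.** The point holds as a mismatch between a hypothesis and its analysis. H3.2 is set at 1 year against self-directed shopping; the only QALY analysis is at 10 years; the other cost-effectiveness measure has no stated horizon and no 12-month BP to rest on; and the SAP has no economic analysis. No specified analysis tests H3.2 at its stated horizon.

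Two open choices are large enough to matter. Counting or not counting the stipend changes incremental cost by $1,500 per participant, a figure taken directly from the protocol. Moving from 1 to 10 years lowers cost per QALY by a factor between 1 and about 10, assuming a one-off cost, no later offsets, and a gain that lasts between 1 and 10 years. The dollar ranges for incremental cost rest on assumed grocery and dietitian prices and serve only to show scale.

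This is a cheap improvement to one hypothesis of a secondary aim. It does not affect the primary SBP analysis or any data collection.

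**What to change.** Amend Protocol section 13, or add a short economic analysis plan, before unmasking:

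1. Make the test of H3.2 a within-trial 12-month incremental cost per QALY, DASH groceries against self-directed shopping, with a confidence interval. Derive utilities from the SF-12 at baseline, 3, 6 and 12 months; area under the curve with bootstrap intervals is one suitable method.
2. State in advance the SF-12-to-utility mapping, the perspective, and the willingness-to-pay threshold. Without a threshold, even a 12-month ratio cannot confirm or refute the hypothesis.
3. Report incremental cost with and without the $1,500 control stipend, and say which version matches the chosen perspective.
4. Keep the 10-year cost per QALY as a labelled modelled projection, with the persistence of the utility gain varied from none beyond 12 months to the full 10 years.
5. Define a prevented hypertension case, the population it applies to and its time point, or limit that measure to 6 months or to the model.

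No new visits or instruments are needed: the SF-12 is already scheduled, the stipend is a fixed amount, and financial records are already a cost source. The cost is protocol wording and modest extra analysis. The downside for the sponsor is that the 1-year ratio may look less favourable than the 10-year one.

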14. DATA MANAGEMENT

Data will be collected from the following main sources: 1) Data collected by trial staff on trial forms for later entry or directly inputted into the data management system(DMS)/REDCap; 2) Data from Quest laboratories electronically available for upload; 3) Data from Spacelabs ambulatory blood pressure monitoring devices available for direct upload; 4) Data from the Automated Self-Administered 24-Hour (ASA24®) Dietary Assessment Tool, estimating the nutrient content of consumed foods, and 5) Data derived from ESHA software, estimating the nutrient content of the intervention; 6) Data collected from self-administered forms; and 7) Data collected via our online Qualtrics (Seattle, Wa) screening survey or a recruitment tracking Excel database. The DMS will be accessible only via the secure website and only to authorized personnel. Data entered into the DMS will be subject to intra- and inter-item checks, such as range checks, logic checks, and consistency checks. Missing data items will be noted in the database, although certain key values (e.g., blood pressure measurement) will not be allowed to be marked 'missing.' Data entry staff will perform data entry as soon as possible after data has been collected (within one week).

Recruitment data for tracking enrollment sources and goals will be managed separately in a secured team folder. All laptops are password protected and encrypted.

Data confidentiality and integrity

The investigative team, including staff at all levels of the study, will be trained in the importance of data integrity and maintaining participant confidentiality, including HIPAA (Health Insurance Portability and Accountability Act). All data will be stored on secure servers. All study-related computers will be located behind appropriate firewalls and will maintain automated virus update mechanisms. Printed materials will be maintained in locked rooms and file cabinets accessible only to the study team. All staff will sign statements attesting to their understanding of and willingness to abide by policies regarding confidentiality and data integrity. Annual Staff Retreats will be conducted for further training on the importance of data integrity.

Trial-wide data release

De-identified trial data will be shared with external investigators on an individual basis through contact with the trials' principal investigator. GoFresh is part of the RESTORE network and will share common data elements as part of this network.

15. COLLABORATIONS

GoFresh and the RESTORE Network

GoFresh is one of five projects that make up the AddREssing Social Determinants TO PRevent HypErtension (RESTORE) Health Equity Research Network. RESTORE will advance the science of health equity to prevent hypertension (HTN) and cardiovascular disease (CVD) with projects focused on the translation of evidence-based interventions for HTN prevention into community-based settings.

The Aims of RESTORE are to:

- **Aim 1.** Work with Black communities to achieve health equity in prevention of HTN by mitigating the negative impact of social determinants of health (SDOH) on BP in Black adults.
- **Aim 2.** Develop and evaluate strategies for implementing evidence-based lifestyle interventions to prevent HTN in Black communities, thereby shifting the blood pressure (BP) distribution lower for the entire U.S. population.
- **Aim 3.** Disseminate findings to policy makers, payors, and stakeholders like state departments of health to ensure sustainability of HTN prevention strategies in Black communities.
- **Aim 4.** Train the next generation of early-career scientists in health equity and CVD research.

As a member of RESTORE, GoFresh has adopted standardized data elements that correspond with other RESTORE projects to enable cross-site comparisons of the various implementation strategies. GoFresh will share de-identified, common data elements with the RESTORE network to facilitate pooled analyses and ancillary studies.

GoFresh and GoFreshRx

GoFresh focuses on adults without treated hypertension. In parallel we are conducting a trial funded by the National Institute of Minority Health and Health Disparities, using a similar intervention and design, focused on Black adults with treated hypertension. Instruments for both trials will be shared to facilitate pooled analysis of data elements.

16. TIMELINE

There are four main phases:

(1) Protocol development and IRB review (year 1, quarters 1-2); (2) Intervention development (year 1, quarters 1-2); (3) Recruitment, randomization, and follow-up (year 1, quarter 3 to year 4, quarter 2); (4) Data analyses and dissemination (year 3, quarter 3 to year 4, quarter 4). Qualitative interviews occur in years 1-3 with analysis in year 4.

Project Years	1			2				3				4				
Calendar Year	10/2021-9/2022			10/2022-9/2023				10/2023-9/2024				10/2024-9/2025				
Quarter	1	2	3	4	1	2	3	4	1	2	3	4	1	2	3	4
Protocol																
Development/																
IRB Review																
Intervention																
Development																
Recruitment,																
Randomization,																
Follow-up																
Data Analysis																
and																
Dissemination																

